4.10 Procedures

4.10.1 Evaluation Time

T0 baseline: Enrolment and start of infiltrative treatment

Week T1: Second infiltrative treatment T2 weeks: Third infiltrative treatment

T6 weeks/FU Follow-up visit
T10 weeks/FU Control visit
T24 weeks/FU Follow-up visit

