4.10.2 Visit Paln

TO BASAL: Enrolment

In the course of daily clinical activity, investigators participating in the Clinical Ivestigation Plan will select subjects with GTPS. The Principal Investigator will be responsible for the correct clinical diagnosis, also making use of the instrumental examinations provided for in the Investigation Plan. Subjects meeting the inclusion and exclusion criteria will thus be identified. After having thoroughly explained the aims, purposes and procedures foreseen by the Investigation Plan, the subject will be proposed to participate in the Investigation itself. Finally, the selected subject will be asked to read the information form and to date and sign the Informed Consent and Consent to the Processing of Personal Data form.

Female subjects will have to provide evidence of a negative pregnancy test in order to be enrolled.

We will then proceed with the objective examination and the collection of the information required by the electronic Data Collection Form appropriately prepared.

This will be followed by:

- pain assessment using the NRS scale;
- assessment of pain using the Modified Harris Hip Score (mHHS) scale;
- clinical assessment of pain on palpation of the trochanter using the NRS scale;
- clinical assessment of stenia in abduction of the lower limb with the dynamometer;
- clinical assessment of phlogistic-degenerative signs by MRI of the peritrochanteric region;

The first infiltration will then be performed by means of ultrasound.

Previous or ongoing pharmacological treatments of any kind will be documented.

In order to monitor the consumption of analgesic (celecoxib 200mg / paracetamol 1000 mg) used during the investigation in the event of the onset of pain, a clinical diary will be given to the subject in which to indicate the day and the dose of drug used.

The enrolled subject will be assigned an identification code of a complex type formed by the progressive enrolment number followed by an alphanumeric code generated by GUNA S.p.a. through *Random Sequence Generator* (www.random.org.)

TO BASAL: Enrolment

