In the course of daily clinical activity, investigators participating in the Survey will select subjects with GTPS. The Principal Investigator will be responsible for the correct clinical diagnosis, also making use of the instrumental examinations provided for in the Investigation Plan. Subjects meeting the inclusion and exclusion criteria will thus be identified. After having fully explained the aims, purposes and procedures foreseen by the Investigation Plan, the subject will be proposed to participate in the Investigation itself. Finally, the selected subject will be asked to read the information form and to date and sign the Informed Consent and Consent to the Processing of Personal Data form.

Female subjects will have to provide evidence of a negative pregnancy test in order to be enrolled.

We will then proceed with the objective examination and the collection of the information required by the electronic Data Collection Form appropriately prepared.

This will be followed by:

- pain assessment using the NRS scale;
- assessment of the Modified Harris Hip Score (mHHS) scale;
- clinical assessment of pain on palpation of the trochanter according to the NRS scale;
- clinical assessment of stenia in abduction of the lower limb with the dynamometer;
- clinical assessment of phlogistic-degenerative signs by MRI of the peritrochanteric region;

The first infiltration will then be performed by means of ultrasound.

Previous or ongoing pharmacological treatments of any kind will be documented.

In order to monitor the consumption of analgesic (celecoxib 200mg / paracetamol 1000 mg) used during the investigation in the event of the onset of pain, a clinical diary will be given to the subject in which to indicate the day and the dose of drug used.

The enrolled subject will be assigned an identification code of a complex type formed by the progressive enrolment number followed by an alphanumeric code generated by GUNA S.p.a. through Random Sequence Generator (www.random.org.)

T1 week:

At 7 days from day 0, the second infiltration will be performed, the use of celecoxib or paracetamol will be assessed through clinical diary analysis and any Adverse Events occurring after the first administration will be evaluated.

T2 weeks:

At 14 days from day 0, the third infiltration will be performed, celecoxib or paracetamol utilisation will be assessed through clinical diary analysis and any Adverse Events occurring since the last administration will be evaluated.

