The occurrence of Adverse Events will be assessed at each visit. All Adverse Events (AEs), Serious Adverse Events (SAEs) and Suspected Serious and Unexpected Adverse Reactions (SUSARs) occurring between the date of signing the Informed Consent and the end of the Clinical Investigation will be recorded and reported.

All data collected will have to be entered by the Principal Investigator or a Co-Investigator identified by the Principal Investigator into the Electronic Data Collection Sheet provided by Guna S.p.a.

In particular, it is planned to obtain a data collection that is schematically described in the following table (Tab. 1), in which the entries to be made at each visit are shown:

PROCEDURE	VISIT	VISIT	VISIT	VISIT	VISIT	VISIT
SPERIMENTALI						
	Т 0	T 1	T 2	T 6/FU	T10/FU	T24/FU
		WEEKS	WEEKS	WEEKS	WEEKS	WEEKS
	enrolment	Visit	Visit	Control visit	Control visit	End of Clinical
	1°	2°	3°			Investigation
	infiltration	infiltration	infiltation			
Clinical diagnosis of	X					
GTPS						
Evaluation of Selection	X					
Criteria						
Signature of informed	X					
consent						
Signature of consent to	X					
personal data						

processing						
Collection of socio-	X					
demographic data						
Medical history	X					
collection						
NRS Evaluation	X			X	X	X
Assessment of pain on	X			X	X	X
palpation according to						
NRS						
mHHS assessment	X			X	X	X
Assessment of stenia in	X			X	X	X
abduction						
Evaluation of phlogistic	X					X
and degenerative signs						
on MRI						
Infiltrative Treatment	X	X	X			
Evaluation of clinical	X	X	X	X	X	X
diary						
Adverse Event	X	X	X	X	X	X
Evaluation (AE/SAE)						

Tab.1 Data collection during the Clinical Investigation Plan

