4.14.2 Secondary End Points

- Evaluation of the NRS score at time weeks 6 and weeks 24 compared to time day 0.
- Evaluation of mHHS score at time weeks 6, weeks 10, and weeks 24 compared to time day 0.

_

- Clinical evaluation of abduction stenia at time weeks 6, weeks 10, and weeks 24 compared to time day 0.
 - [the stenia will be assessed, with the subject standing on the healthy limb, through measurements of the abduction force of the GTPS-affected hip, using a dynamometer]
- Evidence of resolution or decrease in inflammatory and degenerative signs of the peritrochanteric region of the GTPS-affected hip on MRI investigation at weeks 24 compared to day 0.
- Assessment of analgesic drug unit consumption based on clinical diary at day 0, week 1, week 2, weeks 6, weeks 10 and weeks 24.
 - [Celecoxib 200mg cpr 1 tablet/day will be used as a pain killer, in case of onset/recurrence of pain; if the subject is hypertensive or intolerant Paracetamol 1000mg cpr 2 tablets/day].
- Evaluation of the fraction of subjects who drop out of the Clinical Investigation Plan early in relation to Adverse Events (AE/SAE/SUSAR).

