5.2.3 Secondary Endpoints

Foreword: for all continuous variables, an attempt will always be made to use the parametric test; in the case of non-Gaussian distribution (possibly assessed after Shapiro-Wilk tests) or non-

homogeneous variance, an attempt will however be made to modify the variable with the use of a nonlinear transform (logarithm, ladder, etc.) before using the non-parametric equivalents.

The tests provided for the secondary endpoints are:

- NRS score assessment at time weeks 6 and weeks 24 compared to time day0: anova to repeated measures within subject or Friedman test.
- Evaluation of mHHS score time weeks 6, weeks 10, and weeks 24 compared to time day 0. Test Anova to repeated measures within subject or Friedman test.
- Clinical evaluation of stenia in abduction at time weeks 6, weeks 10, and weeks 24 compared to time day 0: Anova at repeated measurements within subject or Friedman's test
- Evidence of resolution or decrease in inflammatory and degenerative signs of the peritrochanteric region of the GTPS-affected hip, on MRI investigation at weeks 24 compared to day 0: Student's t-test for paired data or Wilcoxon test.
- Assessment of analgesic drug unit consumption based on clinical diary at day 0, week 1, weeks 2, weeks weeks 10, and weeks 24 compared to time day 0: repeated measures Anova or Friedman test.
- Assessment of the fraction of subjects leaving the clinical investigational early in relation to Adverse Events (AE/SAE/SUSAR): measurement of absolute and relative frequency and 95% confidence interval.

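### Analgesic use is compared with a day 0 diary value, but on the visible text the diary is first issued at the visit of the first infiltration and defines no pre-treatment consumption

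*Combined protocol and SAP*

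**What the plan says.** The endpoint in section 4.14.2 is: "Assessment of analgesic drug unit consumption based on clinical diary at day 0, week 1, week 2, weeks 6, weeks 10 and weeks 24". Section 5.2.3 analyses it "based on clinical diary at day 0, week 1, weeks 2, weeks weeks 10, and weeks 24 compared to time day 0", by repeated-measures ANOVA or a Friedman test. The number 6 appears to have dropped out of that list; since 4.14.2 includes week 6, I read this as a slip.

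Section 4.10.1 defines the first visit as "T0 baseline: Enrolment and start of infiltrative treatment". Under T0, section 4.10.2 says that, to monitor the analgesic "used during the investigation in the event of the onset of pain, a clinical diary will be given to the subject". Its stated purpose is to serve as a record "in which to indicate the day and the dose of drug used". The same visit description adds: "Previous or ongoing pharmacological treatments of any kind will be documented". Table 1 ("Tab.1 Data collection during the Clinical Investigation Plan") marks the evaluation of the clinical diary at all six visits, T0 included.

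Neither 4.14.2 nor 5.2.3 gives the period over which units are counted at a visit. The list of annexes names the clinical diary as Annex F; the form itself is not among the documents available.

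**The concern.** A change-from-baseline analysis needs a baseline measured before treatment, with the same instrument as the later values. Here the instrument reaches the subject at the visit where treatment starts, and it is meant for use from then on. The planned reference may therefore be empty by construction.

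ANOVA and Friedman are omnibus tests and carry no direction. The direction of any reported effect comes from the contrast with day 0. If that value is an artificial zero, the trial could report increased analgesic use among subjects whose use had fallen. Analgesic use also matters for reading the pain scores, so a misleading result here would affect the interpretation of other endpoints.

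**Working it through.** **1. The plan's own figures.** The plan gives no usage rate, variance or power for this endpoint. Its only sample-size figure belongs to the primary endpoint. Rejecting at 19 or more successes of 49 gives an exact one-tailed alpha of 0.0231 at 25% and power of 0.9573 at 50%, matching the stated 0.023 and 95.7%. Only n = 49 is carried forward.

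**2. Timing.** Table 1 has no visit before T0. Consent, baseline assessments, diary issue and first infiltration all fall at T0. Section 4.10.2 first describes a review of diary entries at day 7. On this text the day 0 value has three possible forms: zero, missing, or an entry for the day of the first infiltration.

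**3. Sign of the contrast if day 0 is zero.** Let Y(i,t) be the units recorded by subject i at time t, with Y(i,t) ≥ 0 and Y(i,0) = 0. Then D(i,t) = Y(i,t) − Y(i,0) = Y(i,t) ≥ 0 for every subject, so neither a mean nor a rank of the differences can point downward. For example, let true use fall from 0.1 to 0.05 units per day:
- true change over 7 days: 7 × 0.05 − 7 × 0.1 = −0.35 units
- planned contrast: 7 × 0.05 − 0 = +0.35 units

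This step needs no assumption about usage.

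**4. Size, by simulation.** All usage inputs are assumptions. Each subject's daily probability of taking one unit is drawn from Beta(m·c, (1−m)·c), with mean m = 0.02, 0.1, 0.3 or 0.5 and c = 1, 2 or 5. There are 49 subjects with complete diaries, 2,000 runs per setting and alpha 0.05. Ranges cover the three values of c.

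| Day 0 reading | Situation | Mean units/day | Result |
|---|---|---|---|
| Zero, then 7-day windows | No true change | 0.1 or more | Rejects in 99.7-100% (ANOVA), 98.6-100% (Greenhouse-Geisser), 99.4-100% (Friedman) |
| Zero, then 7-day windows | No true change | 0.02 | Rejects in 21-40%, 4.5-20.5%, 19-43% (same order) |
| Zero, week 10 contrast (paired t) | True halving from week 6 | 0.1 | Significant rise in 94-99.7%; never a fall |
| Zero, week 10 contrast (paired t) | True halving from week 6 | 0.02 | Significant rise in 3-19%; never a fall |
| Same-day entries at six visits | No true change | all four | Rejects in 0.8-5.2% (ANOVA or Friedman) |
| Same-day entries, week 10 contrast | True halving from week 6 | 0.1 | Fall detected in 15-19% |
| Same-day entries, week 10 contrast | True halving from week 6 | 0.3 | Fall detected in 47-55% |

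If day 0 is missing, there is nothing to compute.

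**5. Counting window (conditional).** The intervals between visits are 7, 7, 28, 28 and 98 days, 168 in all. Dividing by 7 gives 1:1:4:4:14. If units were totalled since the last visit, constant use would produce totals in that ratio. If single-day values or equal windows are used, the problem does not arise.

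**6. Equal 7-day windows without day 0.** With no true change, rejection is 1.3-5.5% (ANOVA), 0.1-5.0% (Greenhouse-Geisser) and 1.8-5.3% (Friedman), so size is controlled to within simulation error.

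**7. Could week 1 serve as baseline?** It follows the first infiltration. If week 1 use were transiently 1.5 times the later level (an assumption) and nothing else changed, week 10 against week 1 shows a significant but spurious fall in 55% of runs at 0.1 units per day and 98% at 0.3.

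**The case against.** The strongest counter-argument is that the diary form has not been seen. It could carry a baseline or look-back field filled in at T0. The Table 1 mark at T0 would fit that, and the medication-history sentence stands directly before the diary paragraph. This limits certainty. A reader might infer that the diary is proven to hold no pre-treatment data; the documents support only that the visible text defines none. The mark in Table 1 does not say what is counted. The medication history has no look-back period or unit count, and neither the endpoint nor the analysis refers to it. The text describes the diary as covering drug used during the investigation.

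Second, the large rejection rates belong to one reading. A reader might infer that the planned test is almost bound to give a false result. Nothing in the documents says that zero will be entered, no usage rate is given, and on the same-day reading test size is preserved.

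Third, the unequal visit intervals may look like a separate error. They are one only if totals since the last visit are used, which the documents do not say.

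Fourth, 4.14.2 might be read as fixing how units are tallied, because one celecoxib tablet a day stands beside "if the subject is hypertensive or intolerant Paracetamol 1000mg cpr 2 tablets/day". That is a dosing instruction, not a counting rule. It makes reporting by drug sensible but does not show a counting error.

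Finally, this is one of six secondary endpoints in an uncontrolled pilot. That bounds the importance of the point without making the reference valid.

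**Conclusion.** The point stands in limited form. As written, 4.14.2 and 5.2.3 rely on a diary reference for which 4.10.1 and 4.10.2 provide no pre-treatment content. The conclusion rests on the timing in the text and, for the zero reading, on a sign argument that needs no usage rate. The simulated percentages only illustrate size; they depend on assumed rates and on which form the day 0 value takes. The consequence ranges from a contrast that can never show a fall, through one that cannot be computed, to one with correct size and low sensitivity. None of the three gives a usable change from baseline. A look-back entry in Annex F would change this, but none is described.

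The primary endpoint and the sample size of 49 are unaffected. With no control arm, even a repaired analysis describes change over time and not a treatment effect. The change should be made, but the trial's main conclusion does not depend on it.

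**What to change.** For this endpoint only, in 4.14.2 and 5.2.3:

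1. Remove diary day 0 as a time point and delete the comparison with it.
2. Report diary-recorded units per day over an equal 7-day window before each of weeks 1, 2, 6, 10 and 24, separately by drug, descriptively with 95% confidence intervals. This also restores week 6 to the list in 5.2.3 and removes any dependence on visit spacing.
3. Label any test across these windows as change during and after treatment. Do not present week 1 as a baseline.
4. If a pre-treatment reference is wanted, add to the T0 medication history a count of units with a stated look-back period, and label it as recall rather than diary data.

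**Cost.** Items 1 to 3 are a wording amendment, submitted to the Ethics Committee under section 5.4. They need no new data, because the diary already records day and dose. The nominal baseline comparison is given up, and the windows use 5 × 7 = 35 of 168 diary days. Per-day rates over the full intervals would use all 168 days, but the Friedman fallback in 5.2.3 then rejects in 5-51% of simulated trials with no true change. Item 4 adds one data item at T0 and carries the usual weakness of recall.

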5.3 Ethical Authorisation

The Clinical Investigation Plan will be submitted to the relevant Ethics Committee for approval.

5.4 Amendments to the Clinical Investigation Plan

Any amendments to this Investigation Plan will be submitted by the Sponsor, in the form of an amendment, to the relevant Ethics Committee for approval.

5.5 Information of the subject

The purposes and modalities of the Investigation will be explained to each subject by means of an information document (Informed Consent), containing what is verbally stated by the clinician. The subject must date and sign the consent document.

A copy of the document will be given to the subject while the original will be kept by the investigator.

5.6 Adverse Events

An Adverse Event is defined as any harmful clinical event that will occur during the course of the clinical investigation in one of the subjects comprising the study population who has undergone one of the treatments in the investigation plan.

MEDANTRO" CLINICAL INVESTIGATION PLAN Version 2.5 of 08 January 2021 MDG2020711

Adverse events will be classified into serious (SAE) non-serious (AE) and Suspected Serious and Unexpected Adverse Reactions (SUSAR).

An Adverse Event is defined as serious if (ICH-GCP DM 15/07/1997):

- it causes the death of the subject involved in the investigation
- places the subject's life in danger
- is such as to require hospitalization
- is such as to require prolonged hospitalization
- is such as to cause permanent or temporary disability
- leads to a congenital anomaly or birth defect

In all other cases, the Adverse Event will be non-serious and will be classified as:

- mild does not interfere with normal activities of daily living and resolves spontaneously;
- moderate, interferes with activities of daily living but resolves spontaneously;
- severe, prevents daily life activities and does not resolve spontaneously.

All personnel who come in contact with study subjects must report Adverse Events reported by subjects to the Investigator, who has a duty to collect all possible data about them.

- Adverse events (AEs) will be reported within 48 h by the Principal Investigator to the Clinical Research Unit of Guna S.p.a, through telephone, email, appropriate form and simultaneously through e-CRF.
- Serious Adverse Events (SAEs) and Suspected Serious and Unexpected Adverse Reactions (SUSARs) will have to be reported to the Sponsor immediately (within 24 h maximum) through telephone, email, appropriate form and simultaneously through e-CRF by the Principal Investigator and communicated to the Ethics Committee and the Ministry of Health.

GUNA S.p.a. Clinical Research Units

[contact]

mail: [contact]

[contact]

[contact]

GUNA S.p.a. Pharmacovigilance Office

[contact]

mail: [contact]

[contact]

The investigator should ensure that procedures are in place to ensure that the event is resolved.

In the case of nonserious Adverse Events (AEs), it is necessary to keep in mind that they can still give rise to serious events, which is why each Adverse Event must be monitored.

Adverse Events that have not yet resolved at the end of the study will be followed up by the Investigator; each subject who has experienced an Adverse Event will be contacted at least once a month after the conclusion of the study for as many months as deemed appropriate.

5.7 Privacy protection

The identities of data subjects will be known only to the Investigators and the Clinical Monitor in charge of monitoring the investigation. Reference will be made to Regulation (EU) 2017/745.

Full respect for the anonymity of the subjects participating in the Clinical study will be ensured. Data collection, data processing, any scientific publications or congress presentations of the results of the Clinical Investigation will be conducted in accordance with the current Privacy Law - Regulation (EU) 2017/745.

5.8 Access to data

In compliance with the regulations in force concerning Clinical Investigations on medical devices, the Institute and the investigators will allow monitoring of the study according to the monitoring plan drawn up by the Sponsor. In addition, they will allow the Competent Authorities direct access to the study documentation being audited.

5.9 Data ownership

All data collected will belong to Guna S.p.a. Milan, Italy, Sponsor of the Clinical study.

Further information on data ownership can be found in the Economic Agreement document.

5.10 Data processing and publication

The results of this study will be summarised and presented in a final report that will aim to draw reliable conclusions regarding the clinical efficacy of the infiltrative treatment of the painful large trochanter syndrome (GTPS) by means of an infiltrative cycle with an injectable MD Tissue *Collagen Medical Device*. The scientific article will then be edited and sent to a peer reviewed journal in the field for publication in order to disseminate the results obtained to the scientific community.

5.11 Financing

This research is financed by GUNA S.p.a.

Please refer to the Economic Agreement for further information.

5.12 Reference Code of Ethics

Reference is made to the Declaration of Helsinki (Fortaleza 64th 2013) and the principles of Good Clinical Practice (GCP) are to be followed (D.leg. 24 June 2003 - n.211 in G.U. n.184 of 09/08/2003).

